#### 7.2. Payment

Not applicable.

## 7.3. Consent

### Cohort 1

Not applicable. UK-Biobank participants have given their consent for their data to be used for research. Individual participants will not be contacted about the study. Consent for the use of their data will be via the UK Biobank access team.

#### Cohort 2 & 3

The submission of a completed questionnaire will be taken as consent to participate in the PAINSTORM Dundee Epidemiology study. Participants will be asked for consent to be contacted about future studies. If this has not been answered on the paper questionnaire the answer will be assumed to be "no". Participants will also be asked for consent to link the data they provide in the questionnaires to routinely collected electronic NHS medical records, held securely by HIC. If this has not been answered on the paper questionnaire the answer will be assumed to be "no".

# 7.3.1. Additional consent provisions for collection and use of participant data and biological specimens in ancillary studies, if applicable

Consent will be sought to allow contact from other researchers within the PAINSTORM consortium carrying out the qualitative work package. This is a separate protocol and participants may be contacted and invited to take part. A separate PIS and consent process will be carried out for this study. Participants are free to decline to take part in qualitative study, this will not affect their participation in PAINSTORM Dundee Epidemiology study.

#### 7.4. Study assessments

The following data will be collected from participants via the PAINSTORM Dundee Epidemiology questionnaire either on-line or in paper format depending on participants' preferences. The main survey will be preceded by a pilot survey of 200 individuals, to test the email and telephone processes and the questionnaire.

Demographics: Age, gender, ethnicity, time in full-time education, working status, household income.

Psychological factors: adverse childhood experiences, hospital stays

Lifestyle: smoking history, alcohol consumption, physical activity

Clinical factors: diabetes/chemotherapy duration, type of diabetes, height and weight

### Questionnaires:

- CPG 3-month average NRS (pain intensity)
- BPI overall average (pain intensity)
- PROMIS SF-4a (depression, anxiety, sleep disturbance, support)

- TIPI (extraversion, agreeableness, conscientiousness, emotional stability, open to new experiences)
- PCS (pain related worrying)
- MNSI (diabetic neuropathy)
- EORTC-CIPN20 (CIPN)
- EQ5D-5L (health related quality of life)

Where available the following data will be collected via data linkage.

Demographics: Social deprivation

Clinical factors: Body Mass Index (BMI), resting heart rate, blood pressure, medical history of cardiovascular disease.

Biomarkers: glucose, HbA1c, creatinine, total cholesterol, high density lipoprotein (HDL)

Genetics: genome wide

Appendix 1 (Section 14.1) shows the schedule of procedures for all cohorts.

#### Cohort 1

Use of previously obtained data only

#### Cohort 2

Participants will be invited to complete the PAINSTORM Dundee Epidemiology questionnaire at baseline and at 18 months.

#### Cohort 3

Participants previously completed two DOLORisk questionnaires 18 months apart. These will be used for baseline and 18-month follow-up for the PAINSTORM Dundee Epidemiology study. Participants will be contacted 72 months after they completed the DOLORisk baseline questionnaire to complete the PAINSTORM Dundee Epidemiology questionnaire.

## 7.5. Long term follow-up assessments

No long-term follow-up is planned, however, all participants consented will be asked if they wish to be contacted about future research.

## 7.6. Withdrawal criteria

All participants are free to withdraw at any time and are not obliged to give reason(s). Where possible, if participant agrees, the reason for withdrawal will be recorded. If a participant withdraws or is withdrawn their data collected up to that point will be retained unless the participant expresses the wish to withdraw their data and or tissue. Those withdrawn, including those lost to follow-up, will be identified and a descriptive analysis of them provided, including the reasons for their loss, if known, and its relationship to treatment and outcome.

#### 7.7. End of study

The end of study is defined as the last participant contact. The Sponsor and/or CI have the right at any time to terminate the study for clinical or administrative reasons.

HRA Template V1.2 March 2016 IRAS 304842

The end of the study will be reported to the Sponsor, REC and NHS R&D Office(s) within 90 days.

A final clinical study report will be submitted to the Sponsor and REC within 1 year of the end of the study.

#### 8. STATISTICS AND DATA ANALYSIS

At baseline and follow-up, the following important phenotypic groups will be identified in each cohort, using data from the PAINSTORM Dundee Epidemiology questionnaire: (1) those without chronic pain; (2) those with chronic non-NeuP; and (3) those with chronic NeuP. These groups will be defined using the chronic pain identification and DN4 items in the questionnaire. Subgroups will also be identified from these three main phenotypes (see section 8.5).

By comparing these groups at baseline and follow-up, we will be able to identify those who have incident NeuP (those who have developed NeuP *de novo* since the baseline questionnaire was completed), resolved NeuP (those who previously had NeuP, but no longer have it) and persistent NeuP (those whose NeuP remains, but may have improved, become worse or remained the same in severity). The lack of previous longitudinal studies on NeuP makes it difficult to estimate the numbers in these groups. In our previous DOLORisk study with GoDARTS (people with diabetes), over 18 months the incidence of NeuP was 10.7% (paper in preparation). In the general population (GS:SFHS) study, the incidence over the same 18-month period was 6.0%. The estimated prevalence of NeuP in people receiving potentially neurotoxic chemotherapy is 30% after one year.

In all cohorts, we will identify the environmental factors (age, gender, ethnicity, lifestyle, socio-demographic and co-morbidity) associated with the presence, incidence, resolution and persistence of NeuP using chi-square testing, and measure their magnitude using regression analysis. We will develop an initial model through regression-based analysis, to distinguish factors independently associated, and also quantify interactions and confounding between factors. Using the high-quality GWAS data available for UK Biobank, SHARE and GoDARTS, case-control studies will identify the genetic factors (single nucleotide polymorphisms [SNP]) associated with chronic NeuP in those with diabetes and those receiving potentially neurotoxic chemotherapy.

Using both the environmental data and the GWAS data we will seek to develop three sub-models/algorithms explaining NeuP and painful peripheral neuropathy among diabetic and chemotherapy patients in UK Biobank, SHARE and GoDARTS:

- a) Genetic model: an additive genetic model based on regression analysis to predict the onset, persistence and/or progression of NeuP, based on significant SNPs in the genome-wide association studies.
- b) *Environmental model*: a regression model to reflect environmental factors and their relationship with NeuP presence, onset, persistence and remission.
- c) Gene-environment interaction model: a regression model with NeuP onset, persistence and/or progression as outcome, and dosage of alleles for each genetic variant as predictors,

adjusting for demographic covariates, with the specific aim of evaluating the interaction between environmental/life course exposures and genetic variants.

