#### 3.3. Primary objective

In people with diabetes, and/or who have received potentially neurotoxic chemotherapy, what clinical, psychosocial, demographic and genetic factors are associated with the presence of NeuP at baseline and onset, worsening or remission of NeuP after follow-up of up to 5 years?

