## 8.2. Sample size calculation

Cohort 1: Assuming a NeuP prevalence of 10% in the general population and 25% in the diabetic population (painful diabetic peripheral neuropathy [DPN]), we will have a sample size of 17,300 NeuP cases and 155,700 no-NeuP controls in the UK Biobank, with 2,714 having painful DPN and 8,141 without painful DPN.

Cohort 2: Assuming the same NeuP prevalence in the diabetic population and a prevalence of 30% in the chemotherapy population (painful CIPN), we will have a sample size of 1,499 painful DPN and 1,600 without painful DPN in SHARE, and 60 with painful CIPN and 140 without painful CIPN.

Cohort 3: In the first DOLORisk questionnaire (which is being used as baseline), 482 participants had NeuP and 1,094 had no-NeuP in GoDARTS, and 45 participants had painful DPN and 130 without painful DPN.

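### Two-wave comparison cannot establish *de novo* neuropathic pain: recurrences are mixed with first onsets and may pull onset associations toward factors for past pain

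*Protocol*

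**What the plan says.** Protocol Section 8 sorts people at each wave into no chronic pain, chronic non-NeuP and chronic NeuP: "These groups will be defined using the chronic pain identification and DN4 items in the questionnaire". It then states: "By comparing these groups at baseline and follow-up, we will be able to identify those who have" one of three kinds of change. The first is "incident NeuP (those who have developed NeuP *de novo* since the baseline questionnaire was completed". The second is "resolved NeuP (those who previously had NeuP, but no longer have it". The third is persistent NeuP.

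Onset carries weight in the plan. The primary objective (Section 3.3) asks about factors associated with "onset, worsening or remission of NeuP after follow-up of up to 5 years", and onset is an outcome in all three models described in Section 8 (genetic, environmental and gene-environment). For scale, Section 8 reports that in GoDARTS "over 18 months the incidence of NeuP was 10.7" per cent and that in the general population study "the incidence over the same 18-month period was 6.0" per cent. Section 8.2 gives the GoDARTS baseline split: "482 participants had NeuP and 1,094 had no-NeuP in GoDARTS".

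**The concern.** Absent at baseline and present at follow-up is not the same as never affected before. Because the plan recognises resolved NeuP, the baseline-negative group can include people between episodes. When their pain returns, the two-wave rule records it as incident.

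Nothing listed in the protocol separates them out. The outcome table (Section 3.4) and the questionnaire items (Section 7.4) cover current pain, its character, sites and severity, together with psychological, lifestyle and demographic factors and the duration of diabetes or chemotherapy. The only past medical history among the linked variables in Section 7.4 is cardiovascular. Section 6.2 sets no exclusions. The incident, resolved and persistent scheme has no class for a return of NeuP. A SAP could add such a class, but it cannot supply history that was never collected.

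Two things are at stake. A rate labelled *de novo* would overstate first onset if past cases carry a higher risk. A factor related to having had NeuP, including a consequence of it such as low mood, could then appear to be related to onset.

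**Working it through.** **The plan's own figure.** The 10.7% GoDARTS incidence cannot be reproduced, because the protocol gives neither its numerator nor its at-risk denominator. It is taken as stated.

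**Are past cases likely among baseline-negatives?**
- Baseline prevalence (Section 8.2): 482/(482 + 1,094) = 482/1,576 = 30.6%.
- Applying 10.7% to the 1,094 without NeuP: 0.107 × 1,094 ≈ 117 new cases in 18 months.
- If prevalence is stable (an assumption), about as many must remit: 117/482 ≈ 24% of cases per 18 months.
- On the same assumption, 117/1,094 = 10.7% of those NeuP-free at month 18 had NeuP at baseline. In Cohort 3 (planned 667, Section 8.1), 667 × 1,094/1,576 ≈ 463 would be NeuP-free at month 18, and 0.107 × 463 ≈ 50 of them would be visible as past cases in the 2017 data.

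So past cases are unlikely to be negligible, although their number is not known.

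**How much could it matter?** Let *h* be the share of baseline-negative people with past NeuP, and *r* the ratio of their risk to first-onset risk. The documents give neither. The assumed ranges are *h* = 5-30% and *r* = 1-4, with the overall risk held at 10.7%.
- Recurrent share of incident cases = *hr*/(*hr* + 1 − *h*)
- First-onset risk = 0.107/(*hr* + 1 − *h*)
- Apparent onset odds ratio (OR): take a factor with 50% exposure and an OR of 2 for past NeuP, but no effect on first onset or recurrence. Each exposure group's risk is first-onset risk × [1 + (*r* − 1) × that group's past-NeuP share].

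| *h* | *r* | Recurrent share | First-onset risk | Apparent onset OR |
|---|---|---|---|---|
| 5% | 1 | 5% | 10.7% | 1.00 |
| 5% | 4 | 17% | 9.3% | 1.10 |
| 10% | 3 | 25% | 8.9% | 1.12 |
| 20% | 3 | 43% | 7.6% | 1.19 |
| 30% | 1 | 30% | 10.7% | 1.00 |
| 30% | 4 | 63% | 5.6% | 1.29 |

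Worked for the last row:
- Recurrent share = 1.2/(1.2 + 0.7) = 0.63, and first-onset risk = 0.107/1.9 = 0.0563.
- Past-NeuP shares of 22.8% (unexposed) and 37.2% (exposed) average 30% with an OR of 2.
- Risks are 0.0563 × (1 + 3 × 0.228) = 0.095 and 0.0563 × (1 + 3 × 0.372) = 0.119, which give an OR of about 1.29.

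The recurrent share does not depend on the overall incidence, so the 6.0% general population figure gives the same shares.

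**The case against.** The best reply is that *de novo* is tied in the text to the baseline questionnaire and may mean only new relative to baseline. On that reading the wording is at fault and the analysis is not. This stands in part. For predicting who among currently NeuP-free people will have NeuP later, including recurrences is a legitimate target. Even so, many readers will take *de novo* as first onset, so the label should go.

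Several stronger inferences are tempting and are not supported:
- **That the hypothesis concerns first onset.** Section 3.1 speaks of developing NeuP and does not say first. The objective is framed as association, and Section 8.4 calls all outcomes exploratory.
- **That onset factors will simply reproduce the factors for past NeuP.** Contamination is diluted. It vanishes at *r* = 1, and nowhere in the assumed range does the apparent OR approach 2.
- **That the recurrent share can be derived from the GoDARTS figures.** One could run a memoryless two-state model back over five years and then multiply by a raised recurrence risk. That model assumes past NeuP does not affect risk, so the two steps contradict each other.
- **That no history can be obtained.** The content of the chronic pain identification questionnaire is not shown, and Section 9.1 plans linkage to routine clinical data. Neither is said to record earlier, resolved NeuP, but neither rules it out.
- **That Cohort 3 is as exposed as Cohort 2.** Its three waves show whether a month-72 case who was NeuP-free at month 18 had NeuP in 2017. That is partial history, because nothing before 2017 is covered.

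**Conclusion.** The point holds in a limited form. The comparison identifies NeuP that was absent at baseline and present at follow-up. It cannot separate first onset from recurrence, so the protocol claims more than its listed data deliver. Bias toward factors for past NeuP is possible but not established. It requires past cases to differ from others in their risk or in the factors that drive it.

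The figures of 5-63% recurrent cases and an apparent OR of 1.00 to about 1.29 illustrate assumed values of *h* and *r* and do not estimate the bias. The calculation that past cases are not negligible rests on stable prevalence, which is uncertain in an ageing diabetes cohort. The exploratory status of the study lowers the stakes but does not make the label accurate.

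**What to change.** - **All cohorts:** name the outcome as NeuP at follow-up among those without NeuP at baseline, and limit conclusions to that.
- **Cohort 2:** add one item to the baseline questionnaire asking whether the person has ever had this type of pain and when it began. Where history is known, report first-onset and recurrent cases separately.
- **Cohort 3:** for onset between months 18 and 72, add a sensitivity analysis that excludes people with NeuP in 2017. This uses data already held. Recall at month 72 should not be relied on, because it would be collected once the outcome is known to the participant.
- **Cohort 1:** it uses existing data, so only the renaming applies unless UK Biobank already holds pain history.

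The cost is some recall error, fewer events in the first-onset analysis, and a questionnaire amendment with the approvals in Section 11.10. The renaming and the Cohort 3 sensitivity analysis need no new data collection.

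### Onset and remission of NeuP are bare changes of group between two waves with no allowance for misclassification, so correlates of presence can pass for predictors of change

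*Protocol*

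**What the plan says.** Section 8 forms three groups at baseline and at follow-up: no chronic pain, chronic non-NeuP and chronic NeuP. "These groups will be defined using the chronic pain identification and DN4 items in the questionnaire". Change is then derived from membership: "By comparing these groups at baseline and follow-up, we will be able to identify those who have incident NeuP", and likewise "resolved NeuP (those who previously had NeuP, but no longer have it". Persistent cases are those still in the NeuP group, whose pain may differ in degree: "but may have improved, become worse or remained the same in severity". No minimum change, confirming wave or adjustment for misclassification is mentioned.

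The same section uses presence, incidence, resolution and persistence side by side as outcomes for chi-square tests and regressions. It carries onset and persistence into the genetic, environmental and gene-environment sub-models.

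Two expected change rates are given. For people with diabetes (GoDARTS), "over 18 months the incidence of NeuP was 10.7" per cent. For the general population (GS:SFHS), "the incidence over the same 18-month period was 6.0" per cent. No remission rate is given, and the section concedes that "The lack of previous longitudinal studies on NeuP makes it difficult to estimate the numbers in these groups". Section 8.2 reports for baseline that "482 participants had NeuP and 1,094 had no-NeuP in GoDARTS". No DN4 cut-off value and no test-retest reliability are printed.

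**The concern.** The primary objective (section 3.3) asks about presence separately from onset, worsening and remission, and the hypothesis (section 3.1) concerns who will develop NeuP. Under the section 8 rule, a person whose true level sits near the boundary can be classed NeuP-free at one wave and NeuP at the next without any change in their condition. Such people are not a random subset: among those classed NeuP-free, they are the ones with the highest underlying level. Anything associated with that level, and so with presence, will also be associated with apparent onset and, inversely, with apparent remission.

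A factor could therefore be reported as predicting development of or recovery from NeuP when it predicts neither. A larger sample does not help; it only makes the artefact more precise.

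**Working it through.** **Inputs.** Baseline prevalence in GoDARTS (section 8.2): 482 / (482 + 1,094) = 482 / 1,576 = 30.6%. Section 8.2 also assumes 25% in diabetes and 10% in the general population. The 10.7% onset rate comes without numerator or denominator and cannot be rebuilt; it is taken here as a proportion of those NeuP-free at baseline. Reliability r is an assumption, 0.80 to 0.95.

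**Model with no true change.** Each person has a stable level plus an independent normal error at each wave, and one cut-off gives prevalence p at both waves. With B the probability of being above the cut-off at both waves:

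- false onset = (p − B) / (1 − p)
- false remission = (p − B) / p

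In terms of kappa (agreement between the two classifications), these equal p(1 − kappa) and (1 − p)(1 − kappa).

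| p | r | kappa | False onset | False remission | False onset / quoted onset rate |
|---|---|---|---|---|---|
| 30.6% | 0.95 | 0.79 | 6.4% | 14.5% | 6.4/10.7 = 60% |
| 30.6% | 0.90 | 0.70 | 9.1% | 20.6% | 9.1/10.7 = 85% |
| 30.6% | 0.86 | 0.65 | 10.7% | 24.3% | 100% |
| 30.6% | 0.80 | 0.58 | 12.9% | 29.3% | above 100% |
| 25% | 0.95 | 0.79 | 5.4% | 16.1% | 5.4/10.7 = 50% |
| 25% | 0.90 | 0.70 | 7.6% | 22.8% | 7.6/10.7 = 71% |
| 25% | 0.80 | 0.57 | 10.8% | 32.4% | about 100% |
| 10% | 0.95 | 0.76 | 2.5% | 22.1% | 2.5/6.0 = 42% |
| 10% | 0.80 | 0.51 | 4.9% | 43.8% | 4.9/6.0 = 82% |

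Check: 0.306 × (1 − 0.65) = 0.107. At 10% prevalence, noise reaches the 6.0% general-population figure only at reliability of about 0.69.

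**Counts in Cohort 3.** Section 8.1 plans 667 people at three time points. At risk of onset: 667 × 0.694 = 463. Expected onsets: 463 × 0.107 = 50. From noise alone: 463 × 0.064 = 30 at r = 0.95 and 463 × 0.091 = 42 at r = 0.90.

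**Effect on associations.** In simulation, a binary factor shifts the stable level by 0.25 SD (presence odds ratio about 1.5) and nobody changes; p = 30.6%.

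| r | Spurious onset OR, group switch | With minimum change | With confirmation at a further wave |
|---|---|---|---|
| 0.80 | 1.35 | 1.28 | 1.42 |
| 0.90 | 1.33 | 1.27 | 1.37 |
| 0.95 | 1.32 | 1.29 | 1.36 |

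The remission odds ratio under the group switch is 0.80 to 0.83. With 463 at risk, the spurious onset association is significant at 5% in 14% (r = 0.90) to 18% (r = 0.80) of analyses.

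**What a minimum change achieves.** The rule tested was a change beyond 1.96 × the SD of the difference due to error. It cuts false onset to 0.9% to 1.8%. With no true change it barely moves the odds ratio, because the few remaining events are still noise. When some true change is added (its amount is an assumption), the spurious onset odds ratio is 1.18 to 1.26 under the group switch and 1.09 to 1.11 under the minimum change, against a true value of about 1.06. The rule works by making false events a small share of all events.

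**The case against.** **This belongs in the SAP.** Section 8.3 announces three analysis plans, and section 8.8 sends missing and spurious data to the SAP. Thresholds and bias analyses are ordinary SAP content, and an unseen SAP may already contain them. That stands as far as the numerical threshold goes. But section 8 does state a rule for change, and a switch of group is valid data under that rule, so section 8.8 does not obviously reach it.

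**All outcomes are exploratory (section 8.4).** This lowers the stakes, since no confirmatory claim is at risk. It does not cure a bias with a known direction in what the outcome measures.

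**The model is simpler than the classification.** The groups rest on a chronic pain item as well as DN4. Someone moving from no chronic pain to NeuP may never have been near a DN4 boundary. No cut-off is printed, so a common one is inferred from the same groups being formed at each wave. Errors positively correlated across waves would shrink the artefact. These points stand and are why the size is given as a range.

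**Stronger readings a reader might infer.**

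- That noise accounts for both the onset and the remission expected. The protocol states no expected remission rate. For onset in diabetes the match depends on an assumed reliability, and the 6.0% general-population rate is not reached anywhere from 0.80 to 0.95.
- That the minimum-change rule should replace the group switch or decide which factors are reported. The odds ratios above do not support that.
- That Cohort 3's third wave can confirm month-18 transitions. It falls at month 72, and 72 − 18 = 54 months is long enough for true remission, which cannot be told apart from noise. In the model, confirmation also raises the spurious odds ratio.

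**Conclusion.** The point holds in limited form. Section 8 defines incident and resolved NeuP solely by a change of group and then models them beside presence. Misclassification near the boundary biases the onset and remission associations toward the presence association: a presence odds ratio of about 1.5 yields a spurious onset odds ratio of about 1.2 to 1.35, with the inverse for remission. High reliability does not remove this.

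Switching without change would make up a substantial share of the 10.7% diabetes onset rate, and all of it at reliability of about 0.86 or lower at 30.6% prevalence. Well below 0.86 the model predicts more onset than was quoted, so there either reliability is higher or its assumptions fail.

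These sizes rest on assumed reliability, independent errors, equal prevalence at both waves and a single underlying score. The documents do not show that the quoted incidence is in fact noise. The change is worth making because the bias has a clear direction and the remedy is cheap.

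**What to change.** Keep the group switch as the main definition of incident and resolved NeuP. Add to section 8, for the onset and remission models:

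1. A pre-specified sensitivity analysis counting only transitions with a DN4 change larger than measurement error. The threshold should be fixed before analysis, with a stated rule for people without chronic pain, who may have no DN4 score.
2. A misclassification (bias) analysis over a stated range of reliability. This matters most in Cohort 2, which has only two questionnaires.
3. A reporting rule. A factor whose onset or remission estimate shrinks materially toward the null under these analyses is described as associated with the presence of NeuP and not as a predictor of change. An estimate that holds is supportive, not proof.
4. In Cohort 3, report how many month-18 transitions persist at month 72 as description only.

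The cost is protocol or SAP wording, one derived variable and one bias analysis, with no new data collection. The downside is fewer events in the sensitivity analysis, and some true small changes will not be counted there.
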